#### **Group comparisons**

The first set of results for the primary and secondary outcomes (section 3.2) will be demonstrated for those that did not initiate a biologic versus those that did (switch, stop, continue) (initiators

Study Protocol: [OPCG-2005] Biologic Usage Patterns, Clinical Outcomes and

Healthcare Resource Utilization (CLEAR)

versus non-initiators). The second set of results will compare the outcome results for patients that stopped or switched versus those that continued.

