#### 1.2 STUDY OBJECTIVES

The objectives of this study are as follows:

1. To describe the demographic and clinical characteristics (including biomarker characteristics), of five severe asthma patient groups based on patterns of biologic initiation (1. Initiated and switched, 2. Initiated and continued, 3. Initiated and stopped, 4. Not initiated but eligible for biologics, 5. Not initiated and not eligible for any biologics)

[figure not shown]

Figure 2 Chart depicting different severe asthma patient groups in CLEAR

\*All patients who have initiated biologics are considered to have met frequent eligibility criteria (eligibility criteria mentioned below)

- 2. To assess the clinical outcomes (e.g., reduction of exacerbations, long-term OCS, asthma control) across the biologic utilization patterns mentioned above
- 3. To assess the healthcare resource utilization (hospitalization, emergency room visits, non-invasive and invasive ventilation) depending upon which biologic is prescribed

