#### Did not initiate:

- Not eligible: Did not meet the criteria for eligibility of biologic therapy and did not initiate any therapy
- Eligible: Eligible for biologic therapy but did not initiate any biologic therapy
- A "frequent-eligibility" criterion of each biologic class will be used to assess eligibility. This
  criterion will be constructed using the results from the ISAR biologic availability survey and
  will be subject to confirmation from the ISAR scientific steering committee (see Table 1 for
  possible criteria per biologic class)

[figure not shown]

Table 1: Frequent-Eligibility Criteria per Biologic Class. Patients who did not initiate biologic therapy and are eligible will meet any of the three criteria for any of the three biologic groups.

	Anti-lgE	Anti-IL5/5R	Anti-IL4/13
Background therapy	Met via ISAR inclusion criteria		
Positive Allergen test	Yes, AND	N/A	N/A
IgE levels	≥ 30 IU/mL, AND	N/A	N/A
BEC	N/A	≥ 150 cells/µL with long- term OCS, OR ≥ 300 cells/µL without long-term OCS, AND	≥150 cells/µL with long-term OCS, OR ≥300 cells/µL without long-term OCS, OR
FeNO	N/A	N/A	≥25 ppb, AND
Exacerbation OR Iong-term OCS	Pre-therapy exacerbation (≥2) OR On long-term OCS	Pre-therapy exacerbation (≥2) OR On long-term OCS	Pre-therapy exacerbation (≥2) OR On long-term OCS

The ISAR enrolment date will mark the start of the outcome period for those who did not initiate biologics while for those who did the index date will be signified by the First Biologic Therapy Start Date. A minimum of 16-weeks of follow-up time post biologic initiation (outcome period) will be applied in alignment with the ERS recommendation for time of biologic response assessment [8]. This is also congruent with the methodology used in the ISAR research project 'Defining and Characterizing Responders to Biologic TrEAtment in Severe AsthMa Patients (BEAM).' To assess the impact of this design, the study will evaluate and report the number of patients that had three types of follow-up data: 1.) <24 weeks, 2.) > 24 weeks to 1-year 3.) >1-year.

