#### 2.3 DATA SOURCE

The ISAR registry is a multi-country, multi-center, observational epidemiologic data repository with retrospective and prospective data of patients treated with 2018 Global Initiative for Asthma (GINA) Step 5 or uncontrolled on GINA Step 4 treatment regimens. ISAR holds standardized, patient-level, fully anonymized data for ~9,654² (as of November 2020) patients with severe asthma from 19 national registries (Argentina, Australia, Bulgaria, Canada, Colombia, Denmark, Greece, India, Ireland, Italy, Japan, Kuwait, Mexico, Saudi Arabia, South Korea, Spain, Taiwan, UAE, UK and United States). The data is collected specifically for severe asthma research. All data contributors enter data via electronic Case Report Forms (eCRF) on a web-based platform customized for real-life data collection or within specialized electronic medical records. The reason for either stopping or switching the first biologic is also collected, when applicable [4]. Patient recruitment started in December 2015 Ethical governance for ISAR is provided by The Anonymous Data Ethics Protocols and Transparency (ADEPT) committee, an independent body of experts and regulators commissioned by the Respiratory Effectiveness Group (REG). The registry's scientific merit is ensured by the ISAR steering committee (ISC) that is made up of 48 severe asthma specialist or database experts from 25 countries (http://isaregistries.org/)

<sup>2 This does not include the 671 patients from the Australian Severe Asthma Network that was received on the 1st of Dec. as it is undergoing data quality assessments at the moment.

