First the demographic and clinical characteristics as mentioned in section 3.1 will be described in detail per group. This will include describing proportions on patients from each group based on their biomarkers, long term OCS (LTOCS) use, baseline demographics such as those outlined in Section 3.1. Next, the significant difference in level of T2 phenotypes and demographic or clinical characteristics (section 3.1) across the five groups will be compared and tested for statistical significance via Chi-square tests for comparison of counts data, and t-test or one-way analysis of variance (ANOVA) for continuous variables. Where appropriate, McNemar tests, paired t-tests will be considered. Statistical significance will be defined as p <0.05. Stata version 14.2 (College Station, TX, USA) will be used to conduct all statistical analyses and data manipulations.

Additionally, comparisons will be made as follows:

Study Protocol: [OPCG-2005] Biologic Usage Patterns, Clinical Outcomes and Healthcare Resource Utilization (CLEAR)

- 1. Switch vs. continue
- 2. Stop vs. continue
- 3. Patient received biologics vs. eligible but did not receive biologics
- 4. Biologic eligible (biologic users+ non-users but who qualify) vs. not eligible.

#### 4.2 OBJECTIVE 2

As there are various factors underpinning the probability of not receiving, receiving, continuing, switching, or stopping a biologic, comparing the clinical outcomes set forth in section 3.2 will need careful consideration. One of the main confounders to consider is the availability and/or accessibility of multiple biologics in a country. Therefore, all countries included in the analysis of assessing the clinical outcomes across biological utilization groups will have at least 2 biologics available in the market (availability defined as licensed in the country) at the time of the patient's enrolment into ISAR (index date). There will be a cut-off date of 01 Jan 2014 for assessment of clinical outcomes to ensure the availability of drugs in the market.

Furthermore, according to the results of objective 1 (pre-therapy or baseline characteristics), before assessing for differences in the clinical outcomes across groups, baseline imbalance will be examined across groups and matched accordingly. Prior to this step, the clinical outcomes of each group will be described.

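### The first set of outcome results pools patients not eligible for any biologic into the controls and starts follow-up on different events in the two groups, so it does not isolate the association of not initiating among eligible patients

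*Protocol*

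**What the plan says.** - **Outcome comparison.** Protocol section 4.2 (Group comparisons) presents the first set of results for "those that did not initiate a biologic versus those that did (switch, stop, continue". It sets no eligibility restriction. The second set compares stopping or switching with continuing.
- **Two kinds of non-initiator.** Section 2.2 divides them into not eligible ("Did not meet the criteria for eligibility of biologic therapy and did not initiate any therapy") and eligible ("Eligible for biologic therapy but did not initiate any biologic therapy"), using Table 1. Section 1.2 counts them as two of the five study groups.
- **Initiators.** The note to Figure 2 in section 1.2 reads: "All patients who have initiated biologics are considered to have met frequent eligibility criteria".
- **Eligible-only contrast.** Section 4.1 lists "Patient received biologics vs. eligible but did not receive biologics" among the Objective 1 comparisons. Section 4.2 does not take it up.
- **Start of follow-up.** Section 2.2: "The ISAR enrolment date will mark the start of the outcome period for those who did not initiate biologics". For initiators it is the start date of the first biologic. Sections 2.1 and 3 define the index date in the same way.
- **Calendar limits.** Section 4.2: "There will be a cut-off date of 01 Jan 2014 for assessment of clinical outcomes". Section 2.3: "Patient recruitment started in December 2015".
- **Handling of imbalance.** Section 4.2 plans standardized mean differences, propensity score matching, a re-check of balance, model adjustment for residual confounders, and possible stratification by eosinophilic grade.

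**The concern.** Section 1 raises the possibility of a subgroup that is eligible for a biologic but does not benefit from one. The comparison that addresses it is initiators against eligible non-initiators. As written, the headline outcome comparison dilutes that control group with patients who fail the criteria for every biologic class and may have a different exacerbation rate for that reason alone.

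The two clocks add a second problem. Starting a biologic is a treatment decision. Entering a registry is an administrative event that can fall anywhere in the course of the disease. A patient who started a biologic before enrolment also had to remain in care long enough to be enrolled.

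A weak, null or adverse first result could then reflect eligibility, calendar period or survival to enrolment, and a reader could not tell which.

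**Working it through.** The protocol gives no sample size, event rate or effect size for this comparison, so there is no figure to reproduce. The check is a reading of the text, followed by an illustration of direction.

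**1. Who is in the control group.** Section 2.2 makes non-initiators the sum of eligible and not eligible patients. Section 4.2 uses all non-initiators. Ineligible patients are therefore included. The asthma control analysis in section 4.2 likewise refers to those who do not initiate, without the split.

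**2. When the clocks start.** The index date is first biologic for initiators and ISAR enrolment for non-initiators. The registry holds retrospective data (section 2.3), so a biologic start can precede enrolment. From 1 January 2014 to 1 December 2015 is 23 months. Any initiator indexed in that span has no non-initiator indexed at the same time, because none could yet have been enrolled. Section 4.2 also labels enrolment as the index date when it checks that two biologics were available. For initiators that conflicts with sections 2.1 and 3.

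**3. Later initiation.** Both non-initiator groups are defined by not starting a biologic. The censoring events in section 4.2 are death, switching, stopping and loss to follow-up; starting a biologic is not among them. The protocol gives no rule for an enrolled patient who starts one later.

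**4. What matching can reach.** Matching follows from the Objective 1 baseline variables. Setting Table 1 against Table 2:

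| Table 1 criterion | In Table 2? |
|---|---|
| Allergen test | Skin prick test only |
| IgE | Yes |
| Blood eosinophils | Yes |
| FeNO | Yes |
| Long-term OCS | Yes |
| Two or more pre-therapy exacerbations | No |

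Eligibility itself is not named as a matching factor or restriction. Balancing covariates does not move either clock.

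**5. Direction of the pooling effect (all inputs assumed).** Let q be the ineligible share of non-initiators and r their exacerbation rate. Assume 2.0 per year in eligible non-initiators and a ratio of 0.70 for initiators against them, so initiators have 2.0 × 0.70 = 1.4 per year. Without adjustment,

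apparent ratio = 1.4 / [(1 − q) × 2.0 + q × r].

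| r per year | q = 0 | q = 20% | q = 40% | q = 60% |
|---|---|---|---|---|
| 0.5 | 0.70 | 1.4/1.7 = 0.82 | 1.4/1.4 = 1.00 | 1.4/1.1 = 1.27 |
| 1.0 | 0.70 | 1.4/1.8 = 0.78 | 1.4/1.6 = 0.875 | 1.4/1.4 = 1.00 |
| 1.5 | 0.70 | 1.4/1.9 = 0.74 | 1.4/1.8 = 0.78 | 1.4/1.7 = 0.82 |
| 2.0 | 0.70 | 0.70 | 0.70 | 0.70 |

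The shift is toward or past the null when r is below 2.0, absent when r equals 2.0, and in the other direction when r is higher. Neither q nor r is in the document, so the table shows how the bias behaves and is not an estimate.

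**The case against.** The strongest defence is that the pooled contrast does not stand alone. Objective 2 covers outcomes across the five patterns, and section 4.2 describes each group's outcomes before matching. Matching, balance checks and adjustment follow. Most Table 1 criteria are in Table 2, and matching may itself remove some ineligible patients. The covariate list can properly be left to an analysis plan. Section 4.2 speaks of association, although the study aim on the title page speaks of effects.

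Much of this stands, and it rules out several stronger readings that a reader might infer:

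- *That the comparison can show nothing about non-initiation.* Matching and adjustment may recover part of the intended contrast.
- *That ineligible means fewer than two exacerbations.* Table 1 combines biomarker criteria with exacerbations or long-term OCS. A patient on long-term OCS with few exacerbations can be eligible, and one with many exacerbations but low biomarkers can be ineligible. A bias computed from an exacerbation cut-off alone does not describe these groups.
- *That 23 months of initiators certainly lack controls.* The 2014 date is a cut-off for assessing outcomes. Reading it as the earliest index date is an inference, and the number of initiators involved is not given.
- *That treating initiators as eligible is an error.* It is a declared convention, and Table 1 awaits steering committee confirmation. Requiring initiators to pass it could drop patients treated under other local criteria or with missing biomarkers.

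The defence does not answer two points. The protocol names no matched or adjusted outcome contrast with eligible non-initiators, although it already lists that contrast for Objective 1. And no planned step aligns time zero.

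**Conclusion.** The point holds in limited form. The first set of outcome results pools ineligible patients into the controls and starts follow-up on different events. Initiators who started before enrolment may have no contemporaneous control and had to stay in care to be enrolled. The planned matching and adjustment may narrow the gap but do not close it, so the comparison does not isolate the association of not initiating among eligible patients.

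The size of the bias is unknown. The direction given for the pooling rests on one assumption, that ineligible patients have fewer exacerbations than eligible non-initiators. The direction of the time-zero and enrolment effects cannot be read from the document. The conclusion about matching rests on Table 2 being the source of covariates. An analysis plan that added pre-index exacerbations would meet that part, but not the choice of control group or the clocks.

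**What to change.** In section 4.2:

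1. Make initiators versus eligible non-initiators the outcome comparison, and report ineligible non-initiators separately.
2. Include pre-index exacerbations and calendar period of the index date in the matching.
3. For biologics started before ISAR enrolment, use delayed entry at enrolment. Add a sensitivity analysis limited to initiations at or after enrolment.
4. Where the data allow, give eligible non-initiators a comparable time zero, such as the date Table 1 is first met at or after enrolment. End their follow-up as non-initiators at any later initiation.
5. Add a sensitivity analysis limited to initiators who meet Table 1 at index.
6. Reconcile the index date wording in section 4.2 with sections 2.1 and 3.

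The cost is a smaller contrast and some extra coding. Delayed entry removes pre-enrolment person-time from the rate model. In the time-to-first-exacerbation model it also removes patients whose first event after starting came before enrolment. Items 4 and 5 need dated eligibility data, and how complete those are should be reported.

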**Primary outcome: Exacerbation** 

An asthma exacerbation will be defined as the occurrence of the following events (ERS/ATS task

force definition):

asthma-related hospital attendance/admission primary care consultation; AND/OR

asthma-related A&E attendance; AND/OR

an acute oral corticosteroid course of 3 days or more

separate recordings of exacerbations within a 14 day period will be treated as the

same exacerbation.

A time-to-event analysis will be performed to analyse the association between utilization pattern and time to first exacerbation with right censoring at the time of death, switching, stopping or loss to follow-up. Kaplan-Meier curves will be used to describe event-free survival over time and comparisons. Conditional Cox regression will be performed with time to the first exacerbation as the outcome variable (y) to estimate Hazard Ratios (HR) with 95% confidence intervals (CI) of the main effect. The proportional hazard assumption will be evaluated visually by means of a log-log

plot of survival.

As the dispersion of the exacerbation data is expected to be high and as this outcome is conditional on the duration of follow-up, we may apply a negative binomial regression (NBR) to estimate the reduced rate of exacerbation (y=annual rate of exacerbation). We switch to a count model to take advantage of all exacerbations at follow up. Group comparisons (e.g. gender, BMI, number of biologics available etc.) will be made if interaction between a group and biologic use pattern is found. We will also run a NBR using the total post-therapy/post-ISAR enrolment

exacerbations.

Secondary outcome: Asthma control

By applying a multinomial regression model (ordered), we will assess the probability or odds of the combined categories partially or controlled versus uncontrolled asthma for those that continue

compared to those that do not initiate or switch or stop.

Secondary outcome: long term oral corticosteroid (OCS) dose

20

Study Protocol: [OPCG-2005] Biologic Usage Patterns, Clinical Outcomes and Healthcare Resource Utilization (CLEAR)

Descriptive data will summarize long term OCS (LTOCS) doses pre and post therapy and ISAR enrolment showing means, standard deviations, medians, IQR, percentage of those who stopped LTOCS altogether at follow up as well as those who decreased their doses to 5 or less miligrams. Generalized linear model (GLM) with generalized estimation equation (GEE) will be applied to estimate the reduced LTOCS dose across groups while accounting for intra-patient correlation.

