**Figure 3 Study Design** 

Health outcomes, such as exacerbations, asthma control status, emergency room visits, hospital visits, OCS dose (rescue and long-term), as well as health resource utilization outcomes (hospital, emergency room visits and non-invasive and invasive ventilation)) will be assessed across biologic usage groups during the outcome period. In ISAR, data on the outcomes are collected as part of routine general health assessments in accordance with respiratory care guidelines and/or recommended medical practice guidelines.

[figure not shown]

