#### 3.2 STUDY OUTCOMES

The following outcomes measures are measured after index date (follow-up visits).

Table 3 Clinical outcomes of interest for objective 2 of the study

Variable Name	Туре	Description
Number of annualized asthma exacerbations 	Count	Annualized number of exacerbations requiring rescue steroids after index date
Asthma control in the past 4 weeks	Categorical	Categorized as controlled, partly controlled, or uncontrolled according to the GINA Asthma Control Criteria/Asthma Control Questionnaire (ACQ-6)/Asthma Control Test (ACT)
Total dose of oral corticosteroids 	Continuous	Label Dose X Frequency X Duration of Use for maintenance OCS between the index date and date of data extraction
Number of hospital admissions	Count	Annualized number of hospital admissions after index date
Number of emergency room visits	Count	Annualized number of emergency room visits after index date

<sup>3 Total number of exacerbations will be calculated between index date and current visit date

<sup>4 If use of SCS started after the index date, total dose will be calculated between start- and end date of use

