v) Biologic therapy: If patient is prescribed biologic therapy.

vi) Others: Asthma education and inhaler use education.

Table S2: International Severe Asthma Registry bolt-on variables

Category	Variables
 	Safety
Severe infection	
 
Infection type
 
Start and end dates
 
Outcome of infection
 
Site of infection
 

Malignancy	
 
Malignancy history, type, stage, status and diagnosis confirmation
 
Start and end dates
 
Outcome of malignancy
 
Site of malignancy
 

Anaphylactic reaction	
 
Likely exposure of the reaction
 
Time to reaction
 
Date of the reaction
 
Outcome of the anaphylactic reaction
 

	Effectiveness
Comorbidities	Osteoporosis: Start date Circulatory system disease Circulatory system disease: Type Circulatory system disease: Start date Glaucoma or cataract disease Gular disease: Type Ocular disease: Type Ocular disease: Start date Obstructive sleep apnoea  Destructive sleep apnoea: Start date Renal failure Renal failure: Start date Renal failure: Start date Peptic ulcer Peptic ulcer: Start date Pneumonia Pneumonia: Start date
Dosage	Pneumonia: Start date     Label dose for oral corticosteroids     Frequency for oral corticosteroids     Label dose for inhaled corticosteroids     Frequency for inhaled corticosteroids

Study Protocol: [OPCG-2005] Biologic Usage Patterns, Clinical Outcomes and Healthcare Resource Utilization (CLEAR)

Exacerbation history	
 
Dates of exacerbations indicated
 
Type of rescue steroid used with label dose, frequency, start and end dates
 

Medication switching	
 
Reason for switch in patient's asthma medication/treatment
 

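### The section 4.2 exacerbation rule lets a single asthma-related hospital attendance or primary care consultation count as an event without worsening or an unscheduled contact, and it is broader than Table 3

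*Protocol*

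**What the plan says.** The subsection of 4.2 on the primary outcome opens with "An asthma exacerbation will be defined as the occurrence of the following events (ERS/ATS task" force definition) and then lists the qualifying events, joined by AND/OR:

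- "asthma-related hospital attendance/admission primary care consultation; AND/OR"
- "asthma-related A&E attendance; AND/OR"
- "an acute oral corticosteroid course of 3 days or more"

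A merging rule follows: "separate recordings of exacerbations within a 14 day period will be treated as the" same exacerbation. The Kaplan-Meier and Cox analyses of time to first exacerbation come directly after this definition, and the negative binomial models follow them.

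Table 3 in section 3.2 describes the annualised outcome differently: "Annualized number of exacerbations requiring rescue steroids after index date". The group-comparison paragraph of section 4.2 points back to section 3.2 for the primary and secondary outcomes, so both descriptions apply to the same endpoint.

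Two other places bear on how events reach the dataset. The text under Figure 3 in section 2.2 says that "data on the outcomes are collected as part of routine general health assessments in accordance with respiratory care guidelines". Table S2 in the appendices lists, among the registry's bolt-on variables, "Dates of exacerbations indicated", together with details of the rescue steroid used.

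**The concern.** Because the items are alternatives, one asthma-related hospital attendance or one primary care consultation is enough for an event. The word acute qualifies only the steroid course. Nothing in the lead-in or the first item separates an urgent visit for deterioration from a planned review, and patients with severe asthma in a registry have planned reviews. Merging within 14 days removes only recordings that lie close together, so reviews spaced further apart stay as separate events.

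The primary outcome is at stake. In the time-to-first-event analysis a single planned visit would end a patient's event-free time. In the count models each such visit would add to the rate. If the two definitions were reconciled by bringing Table 3 into line with the section 4.2 list, this weakness would remain, so it needs its own correction.

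**Working it through.** The protocol ties no event rate, power calculation or sample size to this definition, so there is no stated figure to reproduce. The check is a comparison of the texts, followed by an illustration on assumed rates.

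**Comparison.** Take a planned asthma review with no change in symptoms and no steroid course.

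| Source | Does it qualify? |
|---|---|
| Section 4.2, item 1 (hospital attendance/admission, primary care consultation) | Yes, if read literally |
| Section 4.2, item 2 (A&E attendance) | No |
| Section 4.2, item 3 (acute OCS course) | No |
| Section 3.2, Table 3 (rescue steroids required) | No |
| Table S2 (dates of exacerbations) | Only if someone recorded it as an exacerbation |

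The same contact is therefore an event under one definition of the primary outcome and not under the other.

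**Illustration.** Let r be the true exacerbation rate per year, v the number of planned visits per year lying more than 14 days apart, and f the share of those visits scored as events. Then

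observed rate ratio = (r_init + f × v_init) / (r_non + f × v_non).

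None of these inputs is in the protocol. Assume r_init = 1.0 and r_non = 2.0, so the true ratio is 1.0/2.0 = 0.50.

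| Planned visits per year, initiators vs non-initiators | f = 5% | f = 25% | f = 100% |
|---|---|---|---|
| 4 vs 4 | 1.2/2.2 = 0.55 | 2.0/3.0 = 0.67 | 5.0/6.0 = 0.83 |
| 6 vs 2 | 1.3/2.1 = 0.62 | 2.5/2.5 = 1.00 | 7.0/4.0 = 1.75 |
| 12 vs 2 | 1.6/2.1 = 0.76 | 4.0/2.5 = 1.60 | 13.0/4.0 = 3.25 |

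With f = 0 the ratio stays at 0.50 whatever the visit pattern. Equal contact frequency only dilutes the ratio toward 1. Moving it to 1 or beyond takes more planned contacts among initiators and a material share of them scored as events.

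**Second comparison.** Section 4.2 censors time to first exacerbation at switching or stopping. Until censoring, stoppers, switchers and continuers are all on their first biologic, so a difference in planned contacts after stopping cannot enter this analysis. For the count models the protocol gives no contact frequency by group, and the comparison pools stoppers with switchers, who go on to another biologic. No direction follows.

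**The case against.** The strongest reply is that the registry may never feed planned contacts into the outcome. The merging rule speaks of recordings of exacerbations, not of contacts, and Table S2 has a field for exacerbation dates with steroid details. The variable lists as shown contain no field for individual biologic administrations (only treatment and start/end dates) and none for primary care consultations. Table 3 would also exclude a planned review. All of this stands, and it means the bias may be nil. It does not remove the defect: section 4.2 does not say that only flagged exacerbations count, the date field is a bolt-on variable, and Table 3 is contradicted by the rule directly above the Cox analysis. The statement under Figure 3 shows only that outcomes are gathered at routine assessments, not that those assessments are themselves outcomes.

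The first list item also lacks a separator before the primary care element, possibly from PDF conversion. That leaves the scope of that element uncertain, but hospital attendance is unqualified either way.

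A reader might go further and infer that biologic-administration visits will count as exacerbations and inflate the rate in treated patients. Suppose visits every 4 weeks (52/4 = 13 a year), 5–10% of them scored, true rates of 0.6 and 1.0, and nothing added for non-initiators. The ratio becomes (0.6 + 0.65)/1.0 = 1.25 to (0.6 + 1.3)/1.0 = 1.9. With 8-weekly visits (6.5 a year) it is (0.6 + 0.325)/1.0 = 0.93 to (0.6 + 0.65)/1.0 = 1.25. The documents do not support this as a finding. They give no administration setting, frequency or coding rule, and non-initiators attend routine assessments too, so adding nothing for them is not justified.

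**Conclusion.** The point holds as a fault in the stated definition. The section 4.2 rule is too broad on its face, because planned asthma contacts can meet it, and it conflicts with Table 3.

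The effect on results is conditional. If planned contacts are scored with similar frequency in all groups, the initiator versus non-initiator contrast is diluted toward 1. If initiators have more of them, the result is biased against initiators. If only registry-flagged exacerbations are used, there is no bias from this source. The tabulated ratios illustrate these cases on assumed rates and are not estimates for this study.

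A reader might also infer that continuers are penalised relative to stoppers because they attend more often. That is not established, since time to first exacerbation is censored at stopping or switching. Nor is there a treated arm in the trial sense: these are observational usage groups.

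**What to change.** Use one definition in section 4.2 and Table 3: an event is an acute worsening of asthma with an unscheduled hospital attendance or admission, A&E attendance or primary care consultation, and/or an acute OCS course lasting at least 3 days. State that planned reviews and biologic-administration visits are excluded. Say also whether events are taken from the registry's exacerbation records or derived from contacts.

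If the registry cannot separate planned from unscheduled contacts, keep only admission, A&E attendance and the acute OCS course.

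The cost is about two lines in section 4.2, a matching edit to Table 3 and a filter in the event derivation. The downside is that some mild unscheduled events are lost where contact type is not recorded.
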